Study Protocol and Statistical Analysis Plan

Lab Evaluation of Novel Hearing Aid Coupling Method - ID# 1082

January 30, 2024

NCT05377359

Lab Evaluation of Novel Hearing Aid Coupling Method - ID# 1082

1 Objectives and hypotheses of the clinical investigation

1.1 Purpose of the clinical investigation claims for clinical performance, effectiveness or safety of the investigational device that are to be verified

The study was an exploratory study in which we evaluated a novel coupling method that allows us to take advantage of both open and closed fittings in a single solution and compared this to traditional coupling methods. The various coupling methods were evaluated using two outcome measures: streaming sound quality and situational preference.

1.2 Primary Objective

The primary objective of this study was to determine if participants with mild to moderately-severe SNHLs find an improvement in streaming sound quality under the novel coupling method (state 1) when compared to the novel coupling method (state 2). Additionally, streaming sound quality of the novel coupling method was compared to traditional open and vented domes.

1.3 Secondary Objectives

The secondary objective of this study was to determine how overall preference ratings for streamed stimuli in realistic noise changes when using novel coupling methods while in different states and while the hearing aid mic is on and off.

2 Design of the clinical investigation

2.1 General

2.1.1 Design Type

This study was a single-blinded, single group interventional study where stimulus presentation order was randomized between participants. All participants were subject to each test condition (cross-over). There was no control group. Participants and investigators were always blinded to the programs that were being rated during testing.

The table below indicates the various programs that each participant evaluated.

Primary Objective	Novel Coupling Method – State 1
	Novel Coupling Method – State 2
	Open Domes
	Vented Domes
Secondary Objective	Novel Coupling Method – State 1 – Mic Off
	Novel Coupling Method – State 1 – Mic On
	Novel Coupling Method – State 2 – Mic Off
	Novel Coupling Method – State 2 – Mic On

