2.5.2 Primary Endpoint Analysis

Sound quality ratings were analyzed using ratings on a scale from 1-100. Ratings were transformed to rationalized arcsine units (Studebaker, 1985). Transformed scores were inspected for normality by visual inspection of histogram data, and protected against departures from sphericity using Greenhouse-Geisser corrections to degrees of freedom. Scores were analyzed using a 3x4 repeated measures analysis of

variance (RM-ANOVA) with stimulus (classical, pop, speech) and condition (state 1, state 2, open dome, closed dome) as the within-subjects factors. Significant effects were located using pairwise comparisons with Bonferroni corrections.

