2.5.3 Secondary Endpoint Analysis

Situational preference data were analyzed using a 2x2x2 RM-ANOVA with condition (state 1, state 2), microphone state (on vs. off), and stimulus (music, speech) as within-subjects factors. Data and analysis followed the same treatment procedures as for the sound quality data. A separate RM-ANOVA was run for when participants were focusing on the stream and for focusing on the external environment. Planned contrasts included: comparison of conditions and or microphone states across stimuli, and comparison of conditions and or microphone states within each stimulus. Comparisons between stimuli were not of interest.

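### Does randomising stimulus order leave the order of the coupling conditions and microphone states uncontrolled?

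*Combined protocol and SAP*

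**What the plan says.** Section 2.1.1 of the combined protocol and SAP holds the only statement on randomisation or order: "stimulus presentation order was randomized between participants". The same section describes a cross-over in which each participant met every condition. It says that both participants and investigators were blinded to the program being rated. It introduces its list with "The table below indicates the various programs that each participant evaluated"; the list has four programs for the primary objective and four state-by-microphone programs for the secondary.

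Section 1.2 makes state 1 versus state 2 the main comparison. Section 1.3 asks how "overall preference ratings for streamed stimuli in realistic noise changes when using novel coupling methods while in different states", and with the microphone on or off. Section 2.5.2 specifies the primary RM-ANOVA "with stimulus (classical, pop, speech) and condition (state 1, state 2, open dome, closed dome) as the within-subjects factors". Section 2.5.3 specifies a "2x2x2 RM-ANOVA with condition (state 1, state 2), microphone state (on vs. off), and stimulus (music, speech) as within-subjects factors", run separately for two focus tasks, and adds: "Comparisons between stimuli were not of interest". Neither model has a term for position or sequence. Section 2.2.1 puts both rating tasks in the second visit, of about 2 hours.

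**The concern.** Read with the factor labels of sections 2.5.2 and 2.5.3, the randomisation in section 2.1.1 seems to apply to the wrong factor. It would balance classical, pop and speech over the session, while the objectives compare couplings and microphone settings. Shuffling the material does not move a program to another place in the session.

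Every participant serves as his or her own comparison and there is no control group. Order control is then what separates a coupling effect from fatigue, practice or a shift in how the rating scale is used. If all participants had rated the programs in one sequence, condition would be aliased with position, and neither RM-ANOVA could tell them apart. The state 1 versus state 2 result could then not be attributed to the coupling.

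**Working it through.** The plan gives no figure to reproduce. The check has three parts.

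**1. Wording.** The words stimulus and stimuli occur 7 times: once each in sections 1.3, 2.1.1 and 2.5.2, and four times in section 2.5.3. The 6 uses outside section 2.1.1 all mean streamed material. Section 2.1.1 calls the compared items programs or conditions. So the narrow reading has support, and no other section says how program order was set. But section 2.1.1 is a short design summary. What is presented for rating at any moment is a program together with its material, so the phrase can cover both. The text is ambiguous; it does not show a fixed order.

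**2. Can the exposure be sized?** Number the presentations p = 0 to N−1 and scale by N−1. The share of a linear start-to-end drift that enters a contrast is the difference in mean scaled position between its two levels. N comes from the cells in section 2.5.2 (3 × 4 = 12) and section 2.5.3 (2 × 2 × 2 = 8). The session layouts are assumptions; the documents give none. Table order means the row order of the list in section 2.1.1.

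| Contrast | Assumed layout, program order fixed | Share |
|---|---|---|
| State, primary | 12 presentations, table order, one block per program (block means 1, 4, 7, 10) | (4−1)/11 = 27% |
| State, primary | 12, table order, all programs within each stimulus | 1/11 = 9% |
| State, primary | 12, program blocks, the two states first and last | (10−1)/11 = 82% |
| State, primary | 36 (each of the three ratings in 2.5.1 on its own presentation), table order, programs innermost | 1/35 = 3% |
| State, secondary | 8, table order, program blocks (means 0.5, 2.5, 4.5, 6.5) | (5.5−1.5)/7 = 57% |
| State, secondary | 8, table order, all programs within each stimulus | 2/7 = 29% |
| State, secondary | 16 (8 × 2 focus tasks), focus tasks in separate halves, program blocks in each | 4/15 = 27% |
| State, secondary | 16, both focus tasks inside each program block | 8/15 = 53% |
| Microphone, secondary | 8, table order, program blocks | (4.5−2.5)/7 = 29% |
| Microphone, secondary | 16, focus tasks in separate halves, program blocks in each | 2/15 = 13% |

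If program order was randomised, the expected share is 0 in every layout, by symmetry. If programs were rated side by side rather than in turn, the shares do not apply. For the primary contrast the fixed-order layouts above run from 3% to 82%, and the documents give no drift size to multiply by. The spread reflects the layout chosen and says nothing about this study.

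**3. What would change in each case?**
- Program order randomised or balanced: no expected bias. Omitting a position term costs only precision. Data, models and conclusions stay as planned.
- One order for all: no model term can separate coupling from position. The planned analysis would be the same, and only the interpretation would be narrower.

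In neither case does the analysis plan change.

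**The case for a change.** The strongest case for acting is that the literal vocabulary favours the narrow reading and nothing else fills the gap. Calling the study a cross-over says that everyone met every condition; it names no sequences. Blinding deals with expectation and does not remove drift with position. The exploratory aim lowers the stakes, but a reader still wants to know whether a condition difference can be put down to the coupling. One sentence from the session records would settle it.

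What stands: the wording is ambiguous, and such a sentence would be a useful courtesy in the report.

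What does not stand is the step from ambiguity to defect. Every non-zero share needs a fixed program order, which no section states. The list in section 2.1.1 shows what was evaluated and is not given as a running order. A single sequence for everyone also sits awkwardly with blinded investigators, who could learn it. That is only modest evidence, because the same section also labels the study single-blinded. Finally, the lack of interest in comparing stimuli is stated only for the secondary analysis. In the primary 3 × 4 model stimulus is a full factor, so randomising its order has a purpose there.

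**Conclusion.** No change to the plan follows. Section 2.1.1 leaves a descriptive detail open, and the ordinary reading for a within-subject rating study with blinded programs, that presentations were randomised as a whole, fills it sensibly. On that reading the expected order bias in the state and microphone contrasts is zero and the RM-ANOVAs of sections 2.5.2 and 2.5.3 stand.

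This rests on two points: the documents show no fixed program order, and the randomisation phrase can cover programs as well as material. If session records showed one sequence for all participants, coupling and position could not be separated, and that limit would belong in the interpretation of the results. No percentage should be attached to that possibility, because both the session layout and the size of any drift are unknown.

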2.2 Procedures

2.2.1 Investigation-related Procedure

Recruitment paths:

- Western University's internal database was accessed to see if any potential participants who fit the inclusion criteria were available.
- Referrals from hearing healthcare providers in the London and surrounding area were requested.
- Self-referral from clinical investigation postings.

Tasks:

Appointment tasks are listed in the table below.

Tasks per appointment visit.

Visit 1	Visit 2

• The visit would last approximately 2 hours.• Participants were asked to complete the following:
○ Review and sign study consent form and related forms○ Hearing test was completed (including otoscopy, tympanometry, speech testing (SRT and WRS), and pure-tone threshold testing (air and bone))	
• The visit would last approximately 2 hours.• Participants were asked to complete the following:
○ Streaming sound quality task (primary objective)○ Situational preference task (secondary objective)

2.3 Determination of Sample Size

Sample size was estimated based on a previous version of the study in which the primary outcome was speech in noise recognition. Sample size was estimated using GPower software, for repeated measures ANOVA (Faul et al., 2007; Faul et al., 2009). Past studies in this area have typically used about 20 participants. It should be noted that as a post-market exploration study, a formal sample size estimation for the sound quality evaluation is not mandatory.

2.4 Statistical criteria of termination of trial

n/a

2.5 Planned Analyses

2.5.1 Datasets to be analyzed, analysis population

Datasets to be analyzed:

- Demographic information (e.g., hearing profiles, hearing aid experience, age, etc.) will be analyzed.
- Sound Quality: Subjective ratings (fullness, sharpness, overall preference) (1-100)
- Situational Preference: Subjective ratings (overall preference) (1-100)

2.5.2 Primary Endpoint Analysis

Sound quality ratings were analyzed using ratings on a scale from 1-100. Ratings were transformed to rationalized arcsine units (Studebaker, 1985). Transformed scores were inspected for normality by visual inspection of histogram data, and protected against departures from sphericity using Greenhouse-Geisser corrections to degrees of freedom. Scores were analyzed using a 3x4 repeated measures analysis of

variance (RM-ANOVA) with stimulus (classical, pop, speech) and condition (state 1, state 2, open dome, closed dome) as the within-subjects factors. Significant effects were located using pairwise comparisons with Bonferroni corrections.

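### Does analysing the 1-100 ratings only in rationalized arcsine units make a stimulus-by-condition interaction uninterpretable?

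*Combined protocol and SAP*

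**What the plan says.** Section 2.5.1 lists the primary outcome as "Sound Quality: Subjective ratings (fullness, sharpness, overall preference) (1-100"; situational preference is rated on the same range. Section 2.5.2 then states "Ratings were transformed to rationalized arcsine units", checks the transformed scores by histogram, and fits a 3x4 repeated-measures ANOVA "with stimulus (classical, pop, speech) and condition (state 1, state 2, open dome, closed dome) as the within-subjects factors". Follow-up is stated in one sentence: "Significant effects were located using pairwise comparisons with Bonferroni corrections". Section 2.5.3 carries this over to the 2x2x2 models: "Data and analysis followed the same treatment procedures as for the sound quality data". It adds "Comparisons between stimuli were not of interest".

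The N of the transform is not given, and no analysis on the untransformed scale is described. The primary objective (section 1.2) is whether participants "find an improvement in streaming sound quality under the novel coupling method (state 1) when compared to the novel coupling method (state 2"; comparison with traditional domes is an addition to it. Section 1.1 says "The study was an exploratory study".

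**The concern.** Two things catch the eye. First, the transform is normally written for a score out of N items and its formula needs N, whereas these outcomes are subjective ratings and no N is given. Second, the transform is close to linear in mid-scale but steep near the ends. Both models cross stimulus with condition and therefore test their interaction. If one stimulus is rated near the top, a benefit of the same number of rating points is larger after transformation for that stimulus than for one rated in the middle. A significant interaction could then be reported as a benefit that depends on the stimulus when it reflects only the choice of scale. With no analysis in rating points, the reader would have nothing to check it against.

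**Working it through.** **Inputs.** From the documents: the 1-100 scale, the two factorial models, the Greenhouse-Geisser correction and the Bonferroni follow-up. Assumed, because the documents do not give them: the standard formula of the transform, N = 100, alpha 0.05, all means and SDs, and 20 participants (section 2.3 mentions roughly that number as customary, without computing a size for the ratings). The documents contain no figure to reproduce on this point.

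**The transform.** RAU = (146/π)·[asin√(X/(N+1)) + asin√((X+1)/(N+1))] − 23. At X = 50 and N = 100 the two arcsines sum to π/2, so RAU = 73 − 23 = 50.00. Likewise 60 → 59.26, 82 → 81.90 and 92 → 95.65.

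- Ten rating points from 50: 59.26 − 50.00 = 9.3 RAU. From 82: 95.65 − 81.90 = 13.8 RAU.
- In reverse, ten RAU is 10.8 rating points from 50 but only 7.6 from 82.
- Between 15 and 85, RAU and rating differ by at most 1.1.

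**Sensitivity to N.** Going from 50 to 60 is 9.3, 9.2, 9.0 or 8.5 RAU for N = 100, 50, 25 or 10. Going from 90 to 100 is 25.9, 24.5, 22.4 or 20.5 RAU for N = 100, 50, 20 or 10. N matters mainly at the extreme ends.

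**Interaction test.** Simulated with between-person SD 5, normal errors, and ratings rounded and clipped to 1-100. One condition is raised by 10 units for every stimulus, so there is no interaction on the scale where effects are additive. The table shows the percentage significant at within-person SD 5 / 8 / 12 / 15.

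| Model and stimulus means | Effects equal in | Tested in rating points | Tested in RAU |
|---|---|---|---|
| 3x4; 50, 66, 82 | rating points | 3.4 / 3.6 / 3.9 / 3.5 | 35.2 / 11.3 / 4.7 / 3.6 |
| 3x4; 50, 66, 82 | RAU | 15.7 / 7.4 / 5.0 / 3.9 | 3.2 / 3.3 / 3.2 / 3.2 |
| 2x2x2; 50, 82 | rating points | 5.9 / 6.5 / 7.5 / 7.0 | 69.7 / 30.4 / 10.9 / 6.1 |
| 2x2x2; 50, 82 | RAU | 52.8 / 24.8 / 14.4 / 10.2 | 4.7 to 5.2 |

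With mid-scale means the rates are 3.2-4.3% (3x4; 45, 55, 65) and 4.6-8.6% (2x2x2; 45, 65) on either scale. With high but closer means and effects equal in rating points, the RAU rates are 13 / 6 / 4 / 3% (3x4; 65, 72, 79) and 40 / 16 / 7 / 5% (2x2x2; 65, 80). The effect therefore needs one stimulus near an end of the scale and a small within-person spread.

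**The comparisons the trial asks about.** State 1 versus state 2 over three stimuli (means 50, 66, 82), 5-unit effect, alpha 0.05/6 for the six pairs among four conditions, same SDs:

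- Effects in rating points: power 98.9 / 68.2 / 28.1 / 16.3% in rating points and 98.4 / 65.5 / 27.0 / 16.0% in RAU.
- Effects in RAU: 98.8 / 67.2 / 27.7 / 16.2% and 98.9 / 68.6 / 28.5 / 16.7%.
- Largest gap: 68.2 − 65.5 = 2.7 percentage points. With no effect, both scales reject in 0.6-0.9% of runs, against a nominal 0.83%.

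Within one stimulus at mean 82, +5 points, alpha 0.05: 84.8 / 45.2 / 22.9 / 16.6% in rating points and 83.5 / 44.4 / 23.1 / 16.8% in RAU. With no effect at mean 85: 4.9-5.1% and 4.9-5.4%.

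**The case for a change.** The strongest case for acting is this. The statement that between-stimulus comparisons were not of interest appears only under the secondary endpoint. Section 2.5.2 has no such limit and follows up any significant effect, so a scale-driven interaction in the primary model could be pursued and reported. Under unfavourable inputs the rate is far from trivial: 35% in the 3x4 and 70% in the 2x2x2. The remedy would cost one rerun and one table, and N is needed to reproduce the transformed scores exactly.

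Most of these facts stand; the conclusion does not.

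- What section 2.5.2 prescribes after a significant interaction is pairwise comparison. If conditions are compared within a stimulus, those tests keep their level and power on either scale, as shown above. Only the added claim that the benefit differs between stimuli is exposed, and no objective in sections 1.1 to 1.3 asks for that claim.
- The large rates need means 32 points apart (82 − 50), one of them high, together with an SD of 5. Nothing in the documents shows that this applies.
- A monotone transform cannot reverse the order of conditions within a person's ratings. After averaging over participants this is a strong tendency rather than a guarantee. The doubt is thus confined to interactions in which the order of conditions is preserved.
- Rating points are not the safer reference. When effects are equal in RAU, the analysis in rating points produces the spurious interaction (up to 15.7% and 52.8%). Nothing in the plan makes either scale the true one.

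**Conclusion.** No change to the plan is needed. Using a single scale is a fair trade-off. For ratings bounded at both ends, a transform that stretches the ends is defensible, and every factorial ANOVA on one scale has interactions that depend on that scale. The missing N is a detail an analyst fills sensibly with 100, and over most of the range other values would alter little.

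The size of the issue depends on where the ratings fell. It is negligible for mid-scale ratings. In the 3x4 it is also negligible at a within-person SD of 12 or more; in the 2x2x2 with means of 50 and 82 about 11% remains at SD 12 and 6% at SD 15. It can be substantial at SD 5 with one stimulus near the ceiling. The state 1 versus state 2 comparison and the within-stimulus comparisons are essentially unaffected throughout. A second analysis in rating points would correct no wrong result and would not answer the trial's question better. Since the documents describe the analysis as already done in an exploratory study, it would also be a later addition.

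What remains is ordinary care in reporting: naming N, showing cell means in rating points, and reading an order-preserving interaction near a scale end with caution. All rates rest on the assumed formula, N = 100, 20 participants, alpha 0.05, normal errors and the means and SDs shown.

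### Section 2.5.2 tests State 1 against State 2 validly but inefficiently, as one of the Bonferroni follow-ups to a significant F, with no rating designated; five planned contrasts with Holm would do better

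*Combined protocol and SAP*

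**What the plan says.** Section 1.2 (Primary Objective) asks whether participants "find an improvement in streaming sound quality under the novel coupling method (state 1) when compared to the novel coupling method (state 2"). It then widens the question: "Additionally, streaming sound quality of the novel coupling method was compared to traditional open and vented domes". It does not say which state of the novel coupling is compared with the domes.

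Section 2.1.1 (Design Type) lists State 1, State 2, open domes and vented domes together under the primary objective, without ranking them; it introduces the list with "The table below indicates the various programs that each participant evaluated".

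Section 2.5.1 names three outcomes for this objective, also unranked: "Sound Quality: Subjective ratings (fullness, sharpness, overall preference) (1-100").

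Section 2.5.2 fits a 3x4 RM-ANOVA, stimulus by "condition (state 1, state 2, open dome, closed dome"). Rating is not a factor in the model. The section does not say whether one rating, a composite, or one model per rating is analysed. The follow-up rule is "Significant effects were located using pairwise comparisons with Bonferroni corrections", with no alpha and no list of the comparisons corrected. By contrast, section 2.5.3 does name planned contrasts for the secondary endpoint and sets aside the comparisons that are not of interest.

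**The concern.** The primary objective poses specific comparisons, but the primary analysis has no planned contrast for any of them. Each is tested only if an omnibus effect is significant, and then at a threshold that depends on how many pairs are in the family. Under the usual reading, all condition pairs, part of the error rate goes to dome against dome, which no objective asks about. Single-step Bonferroni also gives up power that a step-down procedure would keep at the same error rate. A moderate real difference between the states, or between a state and a dome, is therefore missed more often than necessary.

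Leaving the rating open works the other way. If each of the three ratings has its own model, each gets its own error rate, and a favourable result on any one could be read as answering the objective. The choice of correction affects neither the estimates nor their standard errors. What is at stake is power, and which p-value counts.

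**Working it through.** **Inputs.** From the documents: four conditions, three stimuli and three ratings (2.1.1, 2.5.1, 2.5.2). No sample size, alpha or effect size is given for sound quality, so there is no planned figure to reproduce. Section 2.3 says only that "Past studies in this area have typically used about 20 participants". Assumed: n = 20, two-sided 0.05, and a paired contrast averaged over stimuli with standardized difference dz (mean difference divided by the SD of the paired differences).

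**Family size.** All condition pairs: 4 x 3 / 2 = 6. Pairs that the objectives ask about: State 1 vs State 2 (1) plus two states x two domes (4) = 5. The sixth pair is dome vs dome.

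**Single-step power.** Noncentral t with n - 1 = 19 df and noncentrality dz x sqrt(20); at dz 0.66 this is 0.66 x 4.472 = 2.95. The threshold per comparison is 0.05/6 = 0.0083 or 0.05/5 = 0.01.

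| dz | 6 pairs | 5 pairs |
|---|---|---|
| 0.5 | 27.3% | 29.7% |
| 0.66 | 51.8% | 54.7% |
| 0.8 | 72.9% | 75.4% |
| 1.0 | 92.1% | 93.2% |

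Dropping dome vs dome alone gains 1 to 3 points.

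**Holm over the five.** Order the five p-values and compare them in turn with 0.05/5, 0.05/4, 0.05/3, 0.05/2 and 0.05, stopping at the first failure. The first step equals Bonferroni over five, so power for a true contrast cannot fall below the right-hand column. Simulation (n = 20, four conditions, equal paired-difference SDs), true contrasts at dz 0.66:

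| Situation | Bonferroni, 6 pairs | Holm, 5 contrasts |
|---|---|---|
| No difference anywhere: familywise error | 4.3% | about 4.4-4.5% |
| Only State 1 differs: State 1 vs State 2 | about 51% | about 59% |
| Only State 1 differs: State 1 vs a dome | about 52% | about 59% |
| Both states differ equally from the domes: state vs dome | about 52% | about 62% |
| Domes lie further away: the contrasts at dz 0.66 | about 52% | about 74-76% |

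The Bonferroni column leaves out the requirement of a significant omnibus F. That requirement can only lower power, so the column does not understate what 2.5.2 delivers under the six-pair reading.

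**Three ratings.** Here the omnibus requirement is applied throughout, as 2.5.2 implies. With no true differences, the chance of at least one false condition pair on one rating is 2.7-2.9%, that is, about 3%. For three independent ratings this predicts 1 - (1 - 0.0268)^3 = 7.8%. Simulation over three ratings gives 7.7% at correlation 0, 7.1% at 0.5 and 5.0% at 0.9.

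**The case against.** The strongest reply is that nothing here is invalid. Bonferroni over all pairs controls the error rate on each rating, State 1 vs State 2 is among the pairs, and all four programs sit under the primary objective, so sharing alpha among them is defensible. The study calls itself exploratory, and section 2.3 adds that "a formal sample size estimation for the sound quality evaluation is not mandatory". For large effects the loss is small (92% power at dz 1.0 even with six pairs). All of this stands, and it keeps the severity low. It does not explain why the primary endpoint lacks the planned contrasts that the secondary endpoint has, or why no rating is named.

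A reader might go further in four ways that the documents do not support:

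- *State 1 vs State 2 should have been tested first at 0.05, with the domes conditional on it.* Section 1.2 adds the dome comparisons without ranking them below the first. Such an ordering would raise power for State 1 vs State 2 to about 80% at dz 0.66. But it would cut state-vs-dome power from about 52% to 3% if the two states perform alike and both differ from the domes.
- *The corrected family was much larger, for example 18 within-stimulus pairs (6 x 3).* The text does not exclude this, but does not say it either.
- *The false-positive rate is 9-14%.* That would apply if State 1 vs State 2 were tested uncorrected at 0.05 on any of three ratings. Section 2.5.2 does not do this.
- *A different dome was tested.* Section 2.5.2 says closed where 1.2 and 2.1.1 say vented. This is an unreconciled label, and nothing shows that the device changed.

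**Conclusion.** The point holds as one of efficiency and clarity. The State 1 vs State 2 test is valid, but weaker than it needs to be at the same error rate. Planned contrasts with Holm over five gain roughly 7 to 10 points of power at dz 0.66 (52% to 59-62%), and more when the domes lie further away, with familywise error below 5% on the designated rating. With no rating designated and one model per rating, the chance of at least one false pair is about 5-8% instead of about 3%.

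These figures rest on n = 20, two-sided 0.05, a six-pair family and equal paired-difference SDs, none of which the documents state. Severity is low to moderate.

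**What to change.** In 2.5.2:

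1. Name five planned contrasts, each averaged over the three stimuli: State 1 minus State 2, and each state minus each dome.
2. Report each estimate with a 95% CI whatever the omnibus F shows.
3. Replace Bonferroni over all pairs with Holm over these five. Report dome vs dome descriptively, outside the corrected family.
4. State which rating carries the test and treat the other two as supportive, or correct across all three (5 x 3 = 15 contrasts). Do not default to overall preference, since nothing in the documents ranks the ratings.
5. Use the ordered test, with State 1 vs State 2 first at 0.05, only if the team states that it ranks that question above the dome comparisons.

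Separately, reconcile the closed dome of 2.5.2 with the vented domes of 1.2 and 2.1.1.

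The cost is a few sentences and five contrasts on existing data. There are three downsides. Unadjusted 95% CIs may not agree with the Holm decisions, and the text should say so. Dome vs dome loses its formal test. And because 2.5.2 reports a completed analysis, any re-run and any choice of rating must be labelled post hoc and shown beside the Bonferroni result already obtained; neither can restore a pre-specified test. Stating which ratings were analysed and which pairs were corrected needs no re-analysis.

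### Must the plan name an effect estimate with a confidence interval for State 1 versus State 2, and document its arcsine transform more fully?

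*Combined protocol and SAP*

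**What the plan says.** Section 1.2 sets the primary question: whether participants "find an improvement in streaming sound quality under the novel coupling method (state 1) when compared to the novel coupling method (state 2". It adds comparisons of the novel method with open and vented domes. Section 1.3 asks a question of size for the secondary outcome: to "determine how overall preference ratings for streamed stimuli in realistic noise changes".

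Section 2.5.1 lists the primary data as "Subjective ratings (fullness, sharpness, overall preference) (1-100". Section 2.5.2 says "Ratings were transformed to rationalized arcsine units", with a literature citation. It then plans a visual check of normality, a 3x4 repeated measures ANOVA (stimulus by condition) with Greenhouse-Geisser correction, and the follow-up step: "Significant effects were located using pairwise comparisons with Bonferroni corrections".

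Section 2.5.3 lists planned contrasts for the secondary outcome and carries the method over: "Data and analysis followed the same treatment procedures as for the sound quality data".

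On sample size, section 2.3 says: "Sample size was estimated based on a previous version of the study in which the primary outcome was speech in noise recognition". It mentions about 20 participants as typical of past studies and notes that a formal estimate for sound quality is not mandatory. Section 1.1 calls the study exploratory.

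**The concern.** The objectives ask whether ratings improve and how they change. The analysis sections answer with significance tests and commit to no estimate or interval, in rating points or in transformed units.

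That gap carries more weight here because the size of the study was not set for sound quality. If State 1 versus State 2 is not significant after correction, the result could mean that the states are alike or that the study was too imprecise to tell. An interval helps to separate the two. If the comparison is significant in transformed units, the reader still does not learn how many points better State 1 was on the scale that participants used.

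The transform adds to the unease. The plan gives no N for converting a 1-100 rating, no formula and no reason, which seems to leave the reader unable to return to rating points.

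**Working it through.** The plan states no figure that can be reproduced: there is no N for this study and no SD, effect size, alpha or power. What follows is illustration on assumed inputs.

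**Inputs**
- n = 20: assumed, from the past-study figure in section 2.3.
- Two-sided alpha 0.05 and a 95% interval: assumed.
- SD of the State 1 minus State 2 difference within participants, 10 to 20 points: assumed.
- Number of comparisons m = 6 (all pairs of four conditions, 4 x 3 / 2) or 18 (6 pairs x 3 stimuli): assumed, since section 2.5.2 does not define the family.

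**Precision**

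Half-width = t(1 - 0.025/m, n - 1) x SD / sqrt(n). For n = 20, t is 2.093 (m = 1), 2.944 (m = 6) and 3.435 (m = 18).

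| SD | 95% half-width (m = 1) | Difference needed, m = 6 | Difference needed, m = 18 |
|---|---|---|---|
| 10 | 4.68 | 6.58 | 7.68 |
| 15 | 7.02 | 9.87 | 11.52 |
| 20 | 9.36 | 13.17 | 15.36 |

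**What an interval would add**

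At SD 15, SD / sqrt(20) = 3.354.
- Observed difference 1 point: t = 0.298, p = 0.769, corrected (x 6, capped at 1) 1.00; interval 1 ± 7.02, or -6.0 to 8.0.
- Observed difference 6 points: t = 1.789, p = 0.090, corrected 0.54; interval 6 ± 7.02, or -1.0 to 13.0.

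Both are non-significant, yet they say different things, so the descriptive value of an interval is genuine.

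**Limits of these figures**

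The planned test is run on transformed scores, and these are paired t calculations on raw points. The planned test has no fixed threshold in points. The thresholds also move with the undefined family, as the last two columns show, and so does power: for a true 5-point difference it is 27.3% / 10.0% / 5.3% (SD 10 / 15 / 20) with m = 6, and 15.6% / 4.8% / 2.3% with m = 18.

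**Does the missing N block conversion to points?**

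The formula is not in the documents. The usual two-term form is assumed: RAU = (146/pi) x [asin sqrt(X/(N+1)) + asin sqrt((X+1)/(N+1))] - 23, with X = N x rating / 100. Rating points equivalent to 5 RAU:

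| Centre of the two ratings | N = 10 | N = 100 |
|---|---|---|
| 50 | 5.89 | 5.43 |
| 80 | 4.89 | 4.36 |
| 90 | 3.89 | 3.30 |

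Moving N from 10 to 100 changes the answer by about half a point (5.89 - 5.43 = 0.46; 3.89 - 3.30 = 0.59). Moving the centre from 50 to 90 changes it by about two points (5.89 - 3.89 = 2.00; 5.43 - 3.30 = 2.13). The obstacle is the curvature of the transform. A mean RAU difference has no single equivalent in points even when N and formula are known. Rating-point differences come from the untransformed ratings, which the analyst has.

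**The case for a change.** The best case for a change is that it costs little and answers the primary question directly. Two people reading the same non-significant result could draw opposite conclusions, and an exploratory study informs later work through estimates and their uncertainty rather than significance labels. A few sentences would commit the sponsor to paired mean differences with intervals from data already in hand, without a new test. This stands as advice on reporting, and the omission it starts from is beyond dispute.

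It does not show that the analysis goes wrong. Silence on estimates does not exclude them: pairwise comparisons after an ANOVA compare means, and reporting those means is the ordinary next step. Naming the transform and citing its source is normal documentation, and the normality check that follows suggests its purpose. The documents do not show that ratings lie near an end of the scale, where the transform would stretch differences most.

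An added commitment would also need care. Averaging State 1 minus State 2 over stimuli could hide an interaction that the 3x4 model can detect. Stopping there would leave out the dome comparisons in section 1.2. An unadjusted interval can exclude zero while the corrected test is not significant: with m = 6 and SD 15, any observed difference between 7.02 and 9.87 points would do so in the raw-point illustration.

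**Conclusion.** No change to the plan is needed. Sections 2.5.2 and 2.5.3 leave a reporting gap that analysts fill sensibly. Followed as written, they give a valid test of State 1 against State 2, and a descriptive interval would not alter that test or its conclusion.

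The stake is readability. On the assumed inputs (n = 20, SD of differences 10 to 20 points) a reader would gain a 95% interval of roughly ±4.7 to ±9.4 points; for n = 15 to 25 the range is ±4.1 to ±11.1. The significance thresholds and power figures rest in addition on raw-point t-tests and an assumed comparison family, so they illustrate the difficulty and do not measure the planned analysis.

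The unstated N is a small documentation point. Supplying it would not let a reader turn a mean RAU difference into rating points.

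The plan describes the work in the past tense, so any estimates in the write-up would be reporting beside the planned tests, best labelled as added afterwards if results are known.
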